4.0 SUMMARY OF PROTOCOL AMENDMENTS

Summary of Protocol Amendments (Substantial and Non-Substantial)				
Amendment	New Protocol	Description of Change	Reason for Change	
Number	Version and			
	Date			
NA	NA	NA	NA	

5.0 PROTOCOL SYNOPSIS

C4d C	
Study Summary	
Protocol Title	Evaluation of Digital Microfluidic Molecular Point Of Care Testing for Respiratory Pathogens Diagnosis
Short Title	Study for Multiplex Assessment and Respiratory Test evaluation; SMART
Study Objectives	To evaluate the analytical performance, turnaround time, operability and acceptability of a novel multiplex respiratory pathogens point of care test device compared to currently available point of care testing.
Study Procedures	Participants will be swabbed to provide samples which will be analysed by standard testing and by the novel multiplex device. The procedures will take place in a single visit in the Emergency Department at Addenbrooke's Hospital in Cambridge. Additional relevant data will be collected from the participants' hospital medical records. No further participant involvement is required.
Study Sponsor	Logilet (UK) Ltd
Sponsor	[name] ([name])
Representative	Product Manager
Study Design	This is a prospective, single centre, single visit, diagnostic performance study. There is no therapeutic agent involved and therefore no randomisation into treatment arms. Two nasopharyngeal swabs will be taken simultaneously from each participant (one from either nostril) and used for Point Of Care Testing using the current gold standard and novel in vitro diagnostic devices. In this way, participants will act as their own controls for comparison of results. If the initial standard test is negative but the participant continues to exhibit clinical symptoms of respiratory infection, a further swab may be taken and tested as per Cambridge University Hospitals NHS Foundation Trust (CUH) policy with another standard device.
Investigational Medical Device	The Logicore System in vitro diagnostic device utilises digital microfluidics to rapidly test for the presence of 6 respiratory pathogens, namely SARS-CoV-2, Influenza A (FluA), Influenza

	Ţ
	B (FluB), Respiratory Syncytial Virus (RSV), Mycoplasma pneumoniae (MP) and human adenovirus (HAdV). The Logicore System produces results in approximately 63 minutes and is expected to feature improved sensitivity when compared to the current gold standard testing device.
Study Location	Cambridge University Hospitals NHS Foundation Trust (CUH)
	Emergency Department
	Addenbrooke's Hospital Cambridge Biomedical Campus
	[name]
	Cambridge
	[name]
Study Duration	When the sample size has been reached, or a maximum of four
Study Duration	months from the time of first participant enrolled to the last
	subject recruited into the study.
Orabia at Danial atian	, i
Subject Population	Male and female participants, of any age, meeting clinically suspected respiratory tract infections case criteria, with a
	signed informed consent form, and who require standard of
	care diagnostic testing as per CUH Trust Infection Prevention
	and Control policy.
Sample Size	400 participants
Sample Size	400 participants
Primary Endpoint	Demonstration of the sensitivity and accuracy of the new
	device compared to current gold standard testing to include
	Positive Predictive Value (PPV), Negative Predictive Value
	(NPV) and sensitivity.
Secondary	1) Comparison of the turnaround time for the new device
Endpoints	compared to gold standard point of care testing.
	2) Evaluation of acceptability of the new device by study
	participants and staff. 3) Targeted Cost Benefit analysis of the new device.
	, i
Reference	UK Medical Devices Regulation 2002 (SI 2002 No 618, as
Standards	amended)
	In Vitro Diagnostic Device Regulation (EU) 2017/746

	 ISO 20916:2019 In vitro diagnostic devices - Clinical performance studies using specimens from human subjects – good study practice Declaration of Helsinki 2024 – Medical Research Involving Human Participants Declaration of Helsinki 2008 – Ethical Principles for Medical Research ICH Guideline E6(R2) 2016: Good Clinical Practice ICH Guideline E8: General Considerations for Clinical Trials
	ICH Guideline E9: Statistical Principles for Clinical Trials
Pandomisation	The time taken to diagnose a patient presenting at the Emergency Department (ED) and initiate appropriate treatment can influence the patient's outcome and disposition. The quicker the therapeutic regime is started, the better outcome for the patient. Furthermore, the sooner the presence of a pathogen is confirmed, the quicker the patient can be appropriately isolated to stem the spread of infection. Current diagnostic testing via the local hospital laboratory (remote to the ED) can take up to an hour and a half from time of swabbing the patient, to receipt of test results. The novel Logicore System device can be used in the ED at the Point of Care (a formal laboratory setting is not necessary) and provides a result in approximately one hour. This device could cut diagnosis time and therefore time to initiation of appropriate treatment, provide better infection prevention control (by identification of those patients that need and do not need isolation measures), streamline the patient treatment pathway and potentially improve outcomes for patients with respiratory infections whilst reducing spread of infection within the hospital. Adopting the Logicore System testing device could benefit patients whilst also benefitting the Trust in terms of reduced economic burden especially in times of winter pressures.
Randomisation	There is no treatment or intervention in this study and therefore no randomisation. Specimens from each participant will be
	The state of the s

tested using gold standard means and the novel device.

Eligibility Criteria	Inclusion Criteria
	1) Male or female
	2) Any age
	3) Presenting to CUH Emergency Department
	4) Symptomatic of respiratory tract infection by clinical evidence of any of the following:
	 Acute respiratory distress syndrome Influenza like illness Fever ≥ 37.8°C
	 Acute onset persistent cough (with or without sputum), hoarseness, nasal discharge or congestion, shortness of breath, sore throat, wheezing or sneezing Any other symptom known to be indicative of acute respiratory episode
	5) Signed consent form for participation
	6) Requiring standard of care diagnostic testing as per CUH Trust Infection Prevention and Control policy
	7) Able to read and/or understand the age-appropriate participant information sheet in English.
	Exclusion Criteria
	Unwilling or unable to comply with study nasopharyngeal swabbing procedures
	Those who are incapacitated or deemed to be lacking capacity to provide informed consent to participate
	3) Prisoners or young offenders.

6.0 ACRONYMS AND DEFINITIONS

Acronym	Definition
ADE	Adverse Device Effect
AE	Adverse Event
APR	Annual Progress Report
CAP	College of American Pathologists
CDC	United States Centers for Disease Control and Prevention

CE	Conformitié Européenne
CEA	
	Cost Effectiveness Analysis
CI COVID 10	Confidence Interval
COVID-19	Coronavirus Disease of 2019
CTCAE	Common Terminology Criteria for Adverse Events v5.0
CUH	Cambridge University Hospitals NHS Foundation Trust
DD	Device Deficiency
DPO	Data Protection Officer
ECDS	Emergency Care Data Set
eCRF	Electronic Case Report Form
ED	Emergency Department
ERS	European Respiratory Society
EU	European Union
FluA	Influenza A
FluB	Influenza B
GCP	Good Clinical Practice
GDPR	General Data Protection Regulation
HAdV	Human adenovirus
HRA	Health Research Authority
HSA	Health Security Agency
ICER	Incremental Cost Effectiveness Ratio
ICF	Informed Consent Form
ICH	International Conference on Harmonisation
IFU	Instructions For Use
IPC	Infection Prevention and Control
IRAS	Integrated Research Application System
ISF	Investigator Site File
ISO	International Organization for Standardization
ITT	Intention To Treat
IVDD	In Vitro Diagnostic Device
IVDR	In Vitro Device Regulation (EU) 2017/746
LOS	Length of Stay
mCTA	model Clinical Trial Agreement
MDR 2002	Medical Devices Regulations 2002 (SI 2002 No 619, as amended)
MHRA	Medicines and Healthcare products Regulatory Agency
MP	Mycoplasma pneumoniae
NA	Not Applicable
NCVR	National Contract Value Review
NEWS-2	National Early Warning Score 2
NHS	National Health Service
NIHR	National Institute for Health and Care Research
NPV	Negative Predictive Value
PCR	Polymerase Chain Reaction
PEWS	Paediatric Early Warning Score
PID	Participant Identifiable Data
1 10	T distribution in abit

PIS	Participant Information Sheet
POC	Point Of Care
POCT	Point Of Care Testing
PPE	Personal Protective Equipment
PPV	Positive Predictive Value
PRC	People's Republic of China
QALY	Quality-Adjusted Life Year
qPCR	Quantitative Polymerase Chain Reaction
REC	Research Ethics Committee
RN	Research Nurse
RSV	Respiratory Syncytial Virus
RT-PCR	Reverse Transcription Polymerase Chain Reaction
SADE	Serious Adverse Device Effect
SAE	Serious Adverse Event
SARS	Severe Acute Respiratory Syndrome
SD	Standard Deviation
SDV	Source Data Verification
SIV	Site Initiation Visit
SOP	Standard Operating Procedure
SUSAR	Suspected Unexpected Serious Adverse Reaction
TMF	Trial Master File
UK	United Kingdom
USADE	Unanticipated Serious Adverse Device Effect
WHO	World Health Organisation

7.0 INTRODUCTION

7.1 Background

Respiratory tract infections are the commonest cause of morbidity and mortality amongst acute infectious diseases¹. The spread of respiratory diseases is quick and poses challenges especially in hospital settings with potentially vulnerable patients. It is, therefore, imperative to expedite diagnosis to facilitate correct and appropriate triage and infection control measures. Rapid turnaround of diagnosis of multiple, frequently occurring respiratory infections also ensures the appropriate treatment and appropriate Infection Prevention and Control (IPC) measures are instituted early upon presentation and detection.

It has been of paramount importance to develop and evaluate diagnostic tests during the COVID-19 pandemic for many reasons; firstly, to diagnose infected cases, so they may be treated appropriately and secondly, to identify cases to quarantine and stop nosocomial transmission. The point-of-care (POC) molecular diagnostic tests have radically improved and changed the way we address the management of these cases.

The standard diagnostic Point Of Care Testing (POCT) by polymerase chain reaction (PCR) usually detects at most 4 respiratory pathogens. Additional PCR testing and United Kingdom Health Security Agency (UK HSA) laboratory analysis may be required, causing obvious bottlenecks, and extended turnaround time. A rapid multiplex POC test is very much needed, that will detect a broader range of respiratory pathogens whilst maintaining a quick turnaround of results, without trading off sensitivity and specificity.

The CUH IPC Guideline² states all symptomatic patients who are to be admitted from ED must have Cepheid monoplex POCT PCR assay performed to test for SARS-CoV-2. During the winter months when there is a high prevalence of seasonal respiratory viruses, a Cepheid multiplex POCT PCR assay is utilised instead which tests for influenza A, influenza B, Respiratory Syncytial Virus (RSV) and SARS-CoV-2. Hospital inpatients who did not exhibit respiratory symptoms at admission but go on to develop them are tested using a SARS-CoV-2 POCT PCR (SAMBA) test and also UK HSA laboratory respiratory PCR swab Luminex analysis which tests for human adenovirus, seasonal coronaviruses, human bocavirus, human metapneumovirus, influenza A (H1, H3, 2009 H1N1), influenza B, parainfluenza (1-4), picornaviruses (rhino/ enterovirus), RSV A and B, *Chlamydia pneumoniae*, *Legionella pneumophila* and *Mycoplasma pneumoniae*. Patients who are admitted to hospital after testing negative on the Cepheid POCT in the ED but with ongoing clinical concern for respiratory viral infection, may also undergo additional UK HSA laboratory respiratory virus PCR testing.

This study aims to recruit participants during the winter months, when the gold standard POCT device used at CUH is the Cepheid multiplex PCR assay (known as GeneXpert). This test can produce results in around 40 minutes to an hour. The advantage of utilising the Logicore System is that it can test for 2 additional pathogens in roughly the same amount of time as Cepheid (it takes 63 minutes to produce the results) but is expected to be more sensitive to the pathogens (for example, the minimum limit of detection is 131 copies/mL for SARS-CoV-2 using Cepheid³ but is expected to be only 100 copies/mL for the same pathogen using the Logicore System). This could alleviate the need for additional UK HSA laboratory testing if a patient was admitted following a negative Cepheid test but continued to exhibit respiratory symptoms, as it is more likely the pathogen would be identified in the initial Logicore System testing process. The CUH IPC Guideline instructs that patients with suspected respiratory infection should be isolated while further UK HSA lab PCR testing is performed. Therefore, the improved sensitivity in diagnostic capability could reduce the need for unnecessary isolation of patients as there would be reduced requirement for the secondary HSA testing. Conversely, the improved turnaround time would ensure rapid instigation of appropriate isolation procedures when a patient has positive initial results to reduce the spread of infection in the ED, in conjunction with quicker treatment of patients with targeted therapeutics medicinal products.

This study aims to produce evidence to support the Logicore System claims of increased sensitivity and specificity, whilst maintaining accuracy, and reduced turnaround times Version 1.0 dated 09/OCT/2025 CONFIDENTIAL Page 13 of 49

compared to current practice, and to provide the Trust with a Cost Benefit analysis from assessment with the Logicore System.

7.2 The Investigational Medical Device

The Investigational Medical Device being assessed in this clinical study is an *in vitro* diagnostic device (IVDD) that has been developed and manufactured by Nanjing Vazyme Biotechnology Company Limited (Vazyme) in the People's Republic of China (PRC). It has already achieved CE marking status in the EU. The CE mark denotes that the device has been produced in accordance with the health, safety and environmental requirements to be sold in the European Economic Area. Logilet (UK) Ltd is the UK subsidiary of Vazyme.

The Logicore System has been certified by the College of American Pathologists (CAP) with 100% detection accuracy for the 6 respiratory pathogens SARS-CoV-2, Influenza A (FluA), Influenza B (FluB), Respiratory Syncytial Virus (RSV), *Mycoplasma pneumoniae* (MP) and human adenovirus (HAdV)].

The Logicore System comprises a portable Operation Module with display screen, an Analytical Module and a Respiratory Pathogen Panel cartridge as shown overleaf:

[figure not shown]

The Respiratory Pathogen Panel containing digital microfluidics is a Class D *in vitro* diagnostic device as defined in the EU In Vitro Device Regulation (IVDR) 2017/746⁴.

The Respiratory Pathogen Panel is inserted into the Analytical Module, and the results are displayed on the portable Operation Module following analysis.

The Respiratory Pathogen Panel cartridge is shown below:

The swab to be tested for presence of respiratory pathogens is placed in a Preservation Buffer (provided to the site by Logilet) and a droplet is then placed in the sample loading chamber of the Respiratory Pathogen Panel cartridge. The Preservation Buffer is stable for 12 months at ambient storage. One Operation Module can be connected to up to 8 Analytical Modules and one cartridge is used per sample. Thus, in this scenario 8 samples can be analysed in approximately one hour. For this clinical study, the site will initially be provided with 2 Operation Modules, to enable 2 Respiratory Pathogen Panel cartridges to be analysed in a one-hour period. If there is sufficient space in the ED, and once the staff are familiar with using the Logicore System, a further 2 Operation Modules (maximum of 4 in total) may be provided to allow 4 cartridges to be analysed at once (i.e. samples from 4 participants).

The Operation Modules are designed to be safely stacked as shown overleaf:

8.0 RISK/BENEFIT ANALYSIS

8.1 Anticipated Risks

During the development and CE marking process, no new unexpected risks were identified for staff using, or participants being tested with, the Logicore System. Whenever a nasopharyngeal swab is used, there is a potential risk of discomfort and/or a small possibility of nosebleed. This will be explained to the participants during the informed consent process and staff are trained in the swabbing procedure to minimise the likelihood of discomfort and/or nosebleeds. The ED research nurse (or designated member of the research team) will wear standard Personal Protective Equipment (PPE) and follow standard measures for cleaning and disinfection to reduce the potential risk of spreading infection between staff and patients, in line with the CUH Infection Control and Prevention Guideline. Furthermore, the Logicore System testing cartridge is fully sealed and the PCR reaction is performed in a silicone oil medium. This double feature minimises risk of contamination and prevents PCR aerosol pollution and bio-hazard risks.

The research staff will be trained to use the Logicore System during the Site Initiation process and will be provided with Instructions For Use to minimise the risk of the device being used incorrectly. Staff will be prompted to check expiry dates to ensure test components are in date and have been stored according to the Sponsor requirements.

8.2 Potential Benefits

The main potential benefits from using the Logicore System device compared to standard testing means are as follows:

- 1) The Logicore System can test for 6 different respiratory pathogens all at once, compared to 4 for the Cepheid GeneXpert device.
- 2) The Logicore System is expected to be more sensitive than the standard device. The minimum limit of pathogen detection is 100 copies/mL whereas the Cepheid GeneXpert device has a minimum limit of detection of 131 copies/mL for SARS-CoV-2³.
- 3) The Logicore System produces rapid results in around one hour, compared to the hour and a half using the UK HSA laboratory second-line test if the initial Cepheid test is negative but clinical symptoms persist.

There is no particular benefit to individual participants from taking part in the study. There are no payments to participants for taking part and the study has no bearing on the clinical care each participant receives. Once the swabs have been taken from participants, they will immediately return to standard clinical care without delay. However, if the Logicore System testing device detects a pathogen that is not identified by the Cepheid test, it may result in faster commencement of treatment with an appropriate therapeutic drug regime. Instigation of treatment will take place outwith the study and will be undertaken by the participant's ED care team. There is no Investigational Medicinal Product in the study itself.

Additionally, participants may experience a sense of altruism from taking part in a study aiming to reduce diagnostic time and spread of infection for future ED patients.

Any risks have been mitigated such that it is considered the benefits to those taking part in the study outweigh any potential risks.

9.0 STUDY OBJECTIVES

9.1 Primary Objective

The primary objective of the study is to demonstrate that the Logicore System multiplex 6 panel respiratory pathogens point of care testing device has increased diagnostic sensitivity when compared to the current gold standard POC multiplex panel at CUH Trust whilst maintaining accuracy, including Positive Predictive Value (PPV), Negative Predictive Value (NPV) and specificity.

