- 1) Very unpleasant
- 2) Slightly unpleasant

- 3) I didn't mind
- 4) I really didn't mind.

Thus, the greater the aggregated score for all participants, the more acceptable the swab process was felt to be.

Each participant will also be asked a second question as follows:

'If you had to have the swab done again, how would you feel about it'?

The participants must give an answer from the following responses:

- 1) Happy
- 2) I wouldn't mind
- 3) Unhappy.

To assess the acceptability of using the Logicore System, ED research team staff will be asked the following question:

'How difficult was the Logicore System to use'?

The staff must rate the Logicore System process according to the following categories:

[figure not shown]
- 1) Very difficult
- 2) Slightly difficult
- 3) Quite easy
- 4) Very easy.

Thus, the greater the aggregated score for all staff, the more acceptable the Logicore System was felt to be.

The study duration will be a one-off face-to-face visit for participants. The Research Nurse or designated member of the ED research team will use the hospital electronic patient record system to obtain the required post-discharge details. Participants will be considered as in the study from the date of signed informed consent form until the date of discharge from the ED. As there is no additional hospital visit required for the study, there is no provision for participant's travel or sustenance expenses, and participants will not be paid to take part in the study.

Figure 1: Sample Collection and Testing Process

If Cepheid and Logicore System results are both positive for the same pathogen, or both negative for all pathogens then the results will simply be recorded.

A. If the Cepheid result is positive but the Logicore System result is negative, the Logicore System test will be classed as a false negative.

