*Table showing impact of variable distribution of infection type on defining sample numbers (after CUH data)

Infection	Estimated Prevalence in	Number Needed for 19
	Winter Population	Positives
RSV	~15%	~127
Flu A	~10%	~190
Flu B	~5%	~380
SARS-CoV-2	~10%	~190

As the basis of this study is to determine sensitivity of the Logicore System testing device, rather than combined diagnostic performance across all four infections (rather than each one separately) then we need to apply this distribution imbalance to the way we calculate the minimum sample number to ensure at least achieving our sensitivity goal for each pathogen.

All eligible participants, i.e. those selected by the respiratory and inclusion criteria noted above with respiratory symptoms and a signed consent form, will be enrolled in the study. Using dual swabs, respiratory samples will be collected simultaneously for use in both new (Logicore System) and gold standard (Cepheid) tests to ensure comparability. This method will reduce the risk that differences in test outcomes are the result of inequitable sampling.

The aim also is to use the inclusion/exclusion criteria to recruit consecutive patients in the ED, suspected of the target condition to attempt to reduce spectrum bias. This real-world sample ensures external validity.

As this POCT occurs in a real time ITT setting, sample swabs will be handled consecutively within a few minutes to enter them into the POCT devices with no delay before and between test commencing. Both devices are expected to deliver a result with a similar elapsed time envelope. Hence commonly both tests will be running in parallel at any moment and model more closely the normal pathways of care in use.

This study is primarily aimed at validating the performance of a new POCT device (Logicore System) against an existing POCT device (Cepheid). This is the basis for this statistical plan rather than using a reference standard/composite diagnostic test e.g. PCR + Chest X-Ray.

Blinding the study will be difficult because of the situation of the study.

With regards to incorporation bias, the new test result will not influence the gold standard result.

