14.2 Study Endpoints

14.2.1 Specificity (or Sensitivity)

The Primary Endpoint is to demonstrate the sensitivity and diagnostic accuracy of the new Logicore System POCT device compared to the current gold standard (Cepheid) for the four overlapping infections. Based on an expected sensitivity of 95% and a 10% allowable margin, approximately 19 positive cases per infection are required to estimate sensitivity with a 95% confidence. Assuming a positivity rate of up to 50% based on the selection criteria, 400 patients will ensure sufficient numbers of true positive cases for each pathogen and enable accurate estimation of sensitivity, specificity and predictive values for both tests. The paired design allows for direct comparison of the new and established test results using McNemar's test and Cohen's Kappa.

As a secondary component we will evaluate turnaround time, patient and staff acceptability of the new test, and Cost-Benefits of the new test device.

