14.5 Statistical Methods

14.5.1 Primary Outcomes

The outcome data from each testing device will be compared against its paired standard to produce 2 x 2 tables for each type of disease

Disease +ve Disease -ve

	Standard positive	Standard negative
Test positive	True Positive (TP)	False Positive (FP)
Test negative	False Negative (FN)	True Negative (TN)

From this we calculate:

i. Sensitivity, Specificity

Sensitivity is the percentage of cases that had the observed outcome was correctly predicted by the model (i.e., TP/(TP+FN).

Specificity is the percentage of observations that were also correctly predicted as not having the observed outcome (i.e., TN/FP+TN).

- ii. Positive Predictive Value
- iii. Negative Predictive Value
- iv. Likelihood Ratios (LR+ / LR-) for the strength of the test versus standard
- v. Accuracy and Cohen Kappa (for agreement)
- vi. If data allows, we intend to model some ROC curves around the various clinical thresholds to ascertain the best use model for this device in this clinical setting.

These core calculations and tests will be performed using JASP software on the recorded data sets.

vii. McNemar's test to compare sensitivity/ specificity.

McNemar's test will be used to assess paired differences in positive and negative results between the new POCT and the established gold standard test for each of the four shared respiratory infections. This test focuses on cases where the two tests disagree, quantifying whether the new test detects significantly more or fewer positive results than the comparator.

For example, among patients tested for RSV, if the new test identifies more positive cases than the gold standard, and this difference is statistically significant on McNemar's test (p < 0.05), this may indicate **superior sensitivity**. Results will be reported with the test statistic, degrees of freedom, and p-value. A similar analysis will be repeated for each infection, supporting the primary endpoint of diagnostic accuracy.

McNemar tests the **null hypothesis** that both tests have the same proportion of positive results by evaluating a test statistic and comparing this with a Chi squared distribution statistic if the value is lower then the null hypothesis is proved.

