14.6 Estimand Table

Objective	Treatment / Strategy	Population	Variable (Outcome)	Intercurrent Events	Summary Measure (Estimand)
Primary: Compare diagnostic sensitivity and accuracy of new POCT vs gold standard for 4 respiratory infections	New POCT vs v gold standard POCT	symptoms meeting	Diagnostic test result (positive/negative) per pathogen	- Invalid swab or test - Withdrawal before testing - Gold standard indeterminate	Difference in sensitivity and specificity; 95% CIs for each; McNemar's test for paired comparisons
Secondary 1: Compare turnaround time from swab to result	New POCT vs gold standard POCT	Same as above	Time (minutes) from sample collection to result availability	- Missing timestamps Result delayed due to user error or system failure	- Mean/median time per method; Paired t-test or Wilcoxon signed-rank test
Secondary 2: Compare specificity of new POCT vs gold standard	Same as above	Same as above	Diagnostic result per pathogen in gold standard negative patients	- Invalid test - Patient lost to follow-up	Specificity per infection type; 95% CI
Secondary 3 & 4: Estimate PPV and NPV of new POCT	New POCT	Same as above	PPV = TP/(TP+FP); NPV = TN/(TN+FN)	- Inconclusive reference test result	PPV, NPV per infection; descriptive analysis with 95% CI
Secondary 5: Assess patient acceptability of new test	New POCT	Patients providing questionnaire data	Self-reported scores on comfort, experience, willingness to retest	- Non-response - Incomplete questionnaire	Median scores; frequencies; thematic analysis for free text

CONFIDENTIAL

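### Sections 11 and 14 define a true case differently for the primary endpoint: under section 14 a sensitivity gain over Cepheid cannot appear, and section 11 checks only one device's extra positives

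*Protocol*

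**What the plan says.** **Aim.** Section 9.1 sets out to demonstrate that Logicore "has increased diagnostic sensitivity when compared to the current gold standard POC multiplex panel at CUH Trust". Section 7.1 repeats the aim, and 14.2.4 states a hypothesis of superior sensitivity for RSV. The primary summary measure in 14.6 is "Difference in sensitivity and specificity; 95% CIs for each; McNemar's test for paired comparisons".

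**Truth in the statistical section.** Section 14.5.1 says: "The outcome data from each testing device will be compared against its paired standard to produce 2 x 2 tables for each type of disease". The columns of that table, labelled as the standard's positive and negative results, serve as diseased and non-diseased. Section 14.1 bases the plan on validation against the existing device and sets aside a reference or composite standard. Section 14.2.1 expects 400 patients to "enable accurate estimation of sensitivity, specificity and predictive values for both tests".

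**Truth in the design section.** Section 11 gives three rules for discordant results:
- Item A: "If the Cepheid result is positive but the Logicore System result is negative, the Logicore System test will be classed as a false negative".
- Item B: if the two devices are positive for different shared pathogens, Cepheid is taken as right.
- Item C: if Cepheid is negative, Logicore positive and the patient still symptomatic, a further swab goes to second-line PCR. A match makes Logicore a true positive; a mismatch makes it a false positive.

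On incorporation bias, 14.1 states that "the new test result will not influence the gold standard result".

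**The concern.** A comparison of two sensitivities needs a truth that neither device supplies. If Cepheid is the truth, it cannot miss a case, so every additional infection that Logicore finds is booked as a Logicore error. Item C replaces that truth for one kind of disagreement only, and section 14 never says how the item C labels enter the 2 x 2 tables.

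Two analysts who both follow the protocol could therefore report opposite answers to the primary question from the same data. A gain found through item C would also rest on unequal scrutiny. Logicore's extra positives can be confirmed, while Cepheid's extra positives are accepted untested.

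**Working it through.** **Inputs.** From 14.1 and 14.3.1: prevalence 5% (Flu B) to 15% (RSV), N = 400, Z = 1.96, P = 0.95, d = 0.10. From 14.5.1: McNemar threshold 0.05, taken as two-sided. The protocol gives no discordant counts and no sensitivity for Cepheid; those used below are assumptions.

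**1. The plan's own figure.** n = 1.96² × 0.95 × 0.05 / 0.10² = 18.25, rounded up to 19; 19 / 0.05 = 380; 380 + 20 = 400. This reproduces. It is a precision calculation for one proportion and contains no difference between devices.

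**2. Notation, per pathogen.** a = both positive, b = Cepheid only, c = Logicore only.

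**3. Truth as in 14.5.1.** Logicore's sensitivity is a/(a+b) and Cepheid's is (a+b)/(a+b) = 1. The difference is a/(a+b) − 1 = −b/(a+b), which is never above 0; c does not enter. Enumerating 102,500 tables (a from 0 to 60, b and c from 0 to 40, at least one Cepheid positive) gave a maximum of 0.00. In 24,670 of those tables the exact McNemar test on raw positives favoured Logicore at p < 0.05, so the two parts of the 14.6 measure can point in different directions.

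**4. Truth as in item C, all c confirmed.** The difference is (a+c)/(a+b+c) − (a+b)/(a+b+c) = (c−b)/(a+b+c), which can be positive.

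**5. The same data read both ways.** RSV, 60 Cepheid positives (15% of 400), b = 0, c = 6:

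| | 14.5.1 | Section 11, item C |
|---|---|---|
| Logicore sensitivity | 60/60 = 100% | 66/66 = 100% |
| Cepheid sensitivity | 60/60 = 100% | 60/66 = 90.9% |
| Difference | 0 | +9.1 points |
| Logicore specificity | 334/340 = 98.2% | 334/334 = 100% |
| Logicore PPV | 60/66 = 90.9% | 66/66 = 100% |

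The exact McNemar p-value is 2 × 0.5⁶ = 0.031. With Flu B (20 Cepheid positives, b = 0, c = 6), item C gives 26/26 against 20/26 = 76.9%, a difference of +23.1 points.

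**6. Dependence on confirmation.** If only 5 of the 6 RSV results are confirmed and the sixth is not counted as a case, the difference is 5/65 = +7.7 points with p = 2 × 0.5⁵ = 0.0625. If 3 are confirmed, it is 3/63 = +4.8 points with p = 2 × 0.5³ = 0.25. One unconfirmed swab changes the test result.

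**7. Size of the distortion on the 14.5.1 reading alone.** Assume 60 true RSV cases, Logicore sensitivity 98%, Cepheid 90%, independent errors and perfect specificity. Then a = 60 × 0.98 × 0.90 = 52.92, c = 60 × 0.98 × 0.10 = 5.88, b = 60 × 0.02 × 0.90 = 1.08. Logicore reads 52.92/54 = 98% against 100%, which is −2 points when the truth is +8. Its PPV reads 52.92/58.80 = 90%. Under these assumptions the apparent difference is always Logicore's sensitivity minus 1, and the apparent PPV equals Cepheid's sensitivity:

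| Assumed Cepheid sensitivity | True difference | 14.5.1 difference | 14.5.1 PPV |
|---|---|---|---|
| 80% | +18 | −2 | 80% |
| 90% | +8 | −2 | 90% |
| 95% | +3 | −2 | 95% |

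**The case against.** **A reader might infer that no data could ever meet the objective.** The protocol does not support that. Item C, echoed in Appendix 1, counts second-line-confirmed Logicore-only positives as true cases, and step 5 shows such a data set. With the assumptions of step 7 and every Logicore-only case confirmed, item C gives 58.80/59.88 = 98.2% against 54/59.88 = 90.2%, or +8.0 points, close to the assumed truth. The −2 figure belongs to the 14.5.1 reading only.

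**The 14.5.1 columns do not name Cepheid.** They refer to a standard, and the composite that 14.1 sets aside is illustrated by PCR plus chest X-ray, not by second-line PCR. Cepheid as sole truth is the likelier reading but not the only one. That strengthens the case for reconciling the sections.

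**McNemar's test is not fixed at zero.** True, and 14.5.1 says only that an excess of positives may point to better sensitivity. But the test compares counts of positives and cannot separate extra true positives from extra false ones.

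**Second-line testing may reach further than item C.** The synopsis, 13.5.4 and Appendix 1 allow it after any negative Cepheid with continuing symptoms, without requiring a positive Logicore. Section 11, however, simply records double negatives, and no rule there sends a Cepheid positive to a second test.

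**A reader might also infer that the incorporation-bias sentence in 14.1 is false.** It is true of the Cepheid result, which comes from a separate swab run in another place. It does not hold for the final truth label under item C, which is assigned only after Logicore is positive.

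**Conclusion.** The point holds as a contradiction on the primary endpoint. If 14.1 and 14.5.1 are followed with Cepheid as the standard, the sensitivity difference cannot favour Logicore, and Cepheid's accuracy is fixed at 100% rather than estimated. If item C is followed, a gain can appear, but the verification behind it is one-sided:
- Items A and B accept every Cepheid positive. Cepheid's specificity and PPV therefore stay at 100% on either reading, and the specificity half of the 14.6 measure cannot favour Logicore.
- Confirmation depends on Logicore's own result, continuing symptoms and a later swab. Section 11 gives no class to a Logicore-only positive that has no second-line swab.
- The second-line panel as listed in 7.1 does not name SARS-CoV-2. If that list is complete, a Logicore-only SARS-CoV-2 positive cannot be confirmed. This is the pathogen for which 7.1 puts figures on the sensitivity claim (100 against 131 copies/mL).

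The gap between readings is 0 against +9.1 points for the RSV example, and PPV 90.9% against 100%. Those sizes rest on assumed counts with all six results confirmed. The upper bound of zero under 14.5.1 rests on no assumption beyond Cepheid being the standard.

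**What to change.** 1. Reconcile sections 11 and 14: state one truth for each table, and say where item C labels enter.
2. Present the Cepheid-referenced tables as positive and negative percent agreement, per pathogen, with 95% confidence intervals. In 14.2.1, remove the claim to estimate accuracy for both devices.
3. Report second-line-resolved discordants in a separate, labelled table. State there that only Logicore-only positives are resolved, how many had a second-line result, and which pathogens the panel covers.
4. Restate 9.1, 10.1 and 14.6 so that no conclusion of superior sensitivity is drawn from the Cepheid-referenced table, from McNemar's test on raw positives, or from one-sided resolution. Align the synopsis and the example in 14.5.1.
5. Keep the incorporation-bias sentence in 14.1 but qualify it: it applies to the Cepheid result, not to the final label under item C.

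**Cost.** The objective, endpoint and estimand are reworded and the primary claim becomes more modest: agreement with Cepheid instead of superiority over it. No extra samples are needed. Keeping a superiority claim would instead require the same verification whichever device is positive, such as one independent reference applied regardless of both results. That would mean additional testing.
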